8.3.4. Efficacy Analyses

All efficacy analyses will be conducted on mITT Population using a 2-sided alpha of 0.05. No adjustment for multiplicity is planned.

The primary endpoint, the change from baseline in DHEAS, will be used to evaluate the preliminary efficacy of tildacerfont therapy relative to placebo and will be summarized using an analysis of covariance (ANCOVA) model with baseline DHEAS as a covariate and randomization strata and dose level as independent variables. Each Treatment Period's final DHEAS assessment (ie, Week 4, Week 8, and Week 12) is the dependent variable. Additional covariates may be added in the SAP.

The proportion of subjects meeting specific DHEAS thresholds will be summarized using exact tests through logistic regression using a similar variable structure as the primary endpoint:

- DHEAS \geq 30% reduction from baseline vs <30% reduction from baseline
- DHEAS \leq ULN vs >ULN.

Additional covariates may be added in the SAP. Missing values for proportion endpoints will not be imputed and will be assumed to be failures.

Exploratory hormone and androgen endpoints will be summarized using an ANCOVA model using a similar variable structure as the primary endpoint. Additional endpoints may be specified in the SAP.

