9.2. Study Discontinuation and Closure

Premature study termination may occur because of a regulatory authority decision, change in opinion of the IRB, drug safety problems, or Sponsor decision. In addition, the Sponsor retains the right to discontinue development of tildacerfont at any time.

Premature study termination will occur if the benefit/risk profile becomes unfavorable because of a new risk or toxicity that makes the study unjustifiable and/or if new scientific evidence that could affect subject safety becomes available during the study (eg, from other clinical trials). When AEs occur, the Sponsor will evaluate the severity, duration, frequency, and nature of the AEs relative to the existing safety profile of tildacerfont to determine whether there are any substantial changes in risk-benefit considerations.

If this study is prematurely terminated or discontinued, the Sponsor will promptly notify the Investigator. After notification, the Investigator must contact all participating subjects within 7 days and have them complete final visit safety assessments. As directed by the Sponsor, all study materials must be collected and all eCRFs completed to the greatest extent possible.

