10.4 Primary Analyses

The primary analyses will be conducted when all subjects complete Week 12 of study treatment and the study and the data has been frozen for analysis.

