13.2 Secondary Efficacy Analysis

The secondary “treatment policy” estimand is the proportion of PCOS subjects with elevated androgens at baseline who were randomized into the study and achieved adequate control of serum DHEAS levels through the 12 weeks of double-blinded, placebo-controlled, dose-escalating Treatment Period. The active arm (dose escalation of tildacerfont from 50 mg QD to 100 mg QD to 200 mg QD) will be compared against the matching placebo group. The placebo treatment group will control for any potential placebo effects in PCOS subjects and their impact on the overall tildacerfont treatment effect. The superiority of tildacerfont is evaluated by comparing the proportion of tildacerfont subjects meeting this criterion is greater than the proportion of placebo subjects meeting this criterion.

Adequate control of serum DHEAS will be evaluated with two measurements: the proportion of subjects with a greater than 30% reduction from baseline and the proportion of subjects with $DHEAS \leq ULN$.

Population: The analysis population for the secondary efficacy analyses is the mITT analysis set, including all randomized PCOS subjects who received at least 1 dose of study drug (tildacerfont or placebo), have at baseline DHEAS assessment, and have at least one post-baseline DHEAS assessment.

Variable: The analysis variable is the proportion of subjects in the mITT analysis set who are responders (defined as [a] $\geq 30\%$ reduction in serum DHEAS or [b] $DHEAS \leq ULN$). This proportion is calculated for each treatment group (e.g., placebo, tildacerfont) as the number of subjects at each time point (Week 12, Week 8, Week 4) who have adequate control of serum hormones (greater than or equal to 30% reduction from baseline [\[2.1\]](#) or $DHEAS \leq ULN$ [\[2.2\]](#)),

divided by the total number of subjects in the mITT analysis who were randomized to that specific treatment.

Subjects with missing data are assumed to be non-responders. Subjects who do not have a 30% reduction from baseline (Objective 2.1) or subjects who have DHEAS > ULN (Objective 2.2) are considered non-responders.

The same analysis will be repeated for subjects with 25% and 20% reduction in DHEAS from baseline.

Intercurrent events: For the secondary analyses, intercurrent events such as treatment interruption or treatment discontinuation will be treated as non-responders, and use of prohibited medications will not be taken into consideration.

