13.2.1.1 Statistical Modeling and Testing

A logistic regression model will be used to evaluate whether the number of subjects who achieve control of DHEAS is different between the tildacerfont treatment groups and the placebo treatment group after 12 weeks of double-blinded, placebo-controlled, dose-escalating treatment. The model will include the responder indicator (Section 9.3.11) as the dependent variable for the Week 12 assessment; treatment group (0 = placebo, 1 = tildacerfont); age as well as baseline DHEAS (for Objective 2.1) or the multiple of baseline DHEAS x ULN (for Objective 2.2) as continuous covariates.

An exact score test derived from the logistic regression model, equivalent to an exact CMH test on small sample sizes, will be used to perform a two-sided test at a significance level of 0.05 to determine whether proportion of responders is different between the tildacerfont treatment group and the placebo treatment group at Week 12. If the logistic model does not converge, three Fisher's exact tests corresponding to tildacerfont compared to placebo will be utilized to assess if differences exist in the proportion of subjects meeting each of the responder criteria.

The statistical model used to characterize the secondary endpoints at Week 12 will also be used to characterize the tildacerfont response at earlier weeks, replacing the Week 12 outcome with the Week 8 and the Week 4 outcome.

Subjects with missing data are assumed to be non-responders in the secondary responder endpoints.

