15 CHANGES RELATIVE TO THE PROTOCOL-SPECIFIED ANALYSIS

The study intended to enroll up to 40 subjects but was discontinued early on the basis of a business decision made by the sponsor. Due to the resulting small sample size, the exploratory efficacy analyses described in Protocol [Section 8.3.4](#) are replaced with summaries of descriptive statistics.

The MMRM analysis introduced in [Section 13.1](#) of this SAP is not mentioned in the protocol. However, to avoid protocol amendment, inclusion of this analysis in the SAP – well in advance of the database lock – is meant to serve the same intent.

The secondary endpoint of 30% reduction from baseline in DHEAS is mentioned in the protocol and sections [6](#), [6.1.2](#), [9.3.12](#) and [13.2](#) of this SAP. However, since some subjects have entered the study up to 25% lower than anticipated DHEAS into the study, it is necessary to assess respond at lower threshold of reduction at 25% and 20% in addition to originally planned 30% reduction.

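### The responder rule makes no exception for women stopped because the sponsor ended the study, so any such woman would be counted as a treatment failure

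*SAP*

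**What the plan says.** SAP 15 says that the study "was discontinued early on the basis of a business decision made by the sponsor". The only analysis change it ties to that decision concerns the exploratory endpoints, which become descriptive: "Due to the resulting small sample size, the exploratory efficacy analyses described in Protocol" section 8.3.4 are replaced. It gives no stopping date, no number enrolled and no number still on treatment at the stop.

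The responder rules are unconditional:
- SAP 13.2, on intercurrent events: "intercurrent events such as treatment interruption or treatment discontinuation will be treated as non-responders".
- SAP 13.2.1.1: "Subjects with missing data are assumed to be non-responders in the secondary responder endpoints". Table 3 in SAP 9.3.12 codes missing as 0.
- Protocol 8.3.4: "Missing values for proportion endpoints will not be imputed and will be assumed to be failures".
- The denominator, in SAP 13.2, is the whole arm: responders are "divided by the total number of subjects in the mITT analysis who were randomized to that specific treatment".

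On what happens to enrolled women when a study ends early, Protocol 6.2 lists termination by the sponsor among the reasons for withdrawing a subject. Protocol 9.2 says that after notification "the Investigator must contact all participating subjects within 7 days and have them complete final visit safety assessments". SAP 10.4, however, states: "The primary analyses will be conducted when all subjects complete Week 12 of study treatment". The opening of SAP 13 likewise places the efficacy analyses after every subject has finished 12 weeks.

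**The concern.** Scoring a discontinuation as non-response is defensible when the reason may reflect the drug: intolerance, lack of effect, or a withdrawal of unknown cause. A business decision says nothing about a woman's DHEAS. Under the present wording, a woman who was responding at Week 8 and was closed out in Week 9 becomes a Week 12 failure.

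If this happened at a similar rate in both arms, both Week 12 response rates and the difference between them would be too low in expectation. The label does not help: SAP 13.2 calls the estimand treatment policy, while scoring discontinuation as failure is a composite strategy. The same woman would also be handled differently in the primary analysis, where SAP 13.1.1 disregards these events and SAP 13.1.3.2 does not impute missing DHEAS.

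At stake is the size of the secondary responder result, mainly at Week 12, which is the 200 mg period.

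**Working it through.** **1. The plan's own figure.** The only sample size in the documents is for the primary endpoint (Protocol 8.1, SAP 7): difference 164, SD 154, two-sided alpha 0.05, 80% power, 2:1 allocation. Placebo n = (1.960 + 0.842)² × 154² × (1 + 1/2) / 164² = 10.4, rounded up to 11. With 22 on tildacerfont the total is 33, and 33/0.85 = 38.8 gives 39. Both figures reproduce. Power at 22/11 is 82.2% by the normal approximation and 79.8% by noncentral t. No response rate or power is given for the responder endpoints, so the rates below are assumptions.

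**2. Formula.** Let c_T and c_P be the shares of mITT women in each arm who miss a visit only because the sponsor stopped, independently of response. Under the written rule the expected difference is p_T(1 − c_T) − p_P(1 − c_P). If c_T = c_P = c, this is (1 − c)(p_T − p_P). Leaving those women out of both numerator and denominator keeps the expectation at p_T − p_P.

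**3. A range for c.** Assume even accrual over 40 to 64 weeks and close-out of everyone on treatment at the stop.
- Women on treatment at the stop: 12/64 to 12/40, or 19% to 30% of those randomised.
- The mITT set (SAP 8.2) needs a post-baseline DHEAS. SAP Table 7 schedules DHEAS at Day 1 and Weeks 4, 8 and 12, and none at the early termination visit. Women stopped before Week 4 therefore normally leave mITT and are not scored as failures.
- Week 12 share of mITT: (12 − 4)/(64 − 4) = 8/60 = 13%, to (12 − 4)/(40 − 4) = 8/36 = 22%.
- Week 8 share, by the same reasoning: 4/60 = 7% to 4/36 = 11%.

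**4. Effect on the estimate**, with assumed rates of 50% and 10% (true difference 40 points):

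| c, both arms | Expected difference |
|---|---|
| 0% | 40 points |
| 13% (8/60) | 0.867 × 40 = 34.7 |
| 22% (8/36) | 0.778 × 40 = 31.1 |

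**5. Unequal cut-off.**
- c_T = 40%, c_P = 0%: 0.30 − 0.10 = 20 points.
- c_T = 0%, c_P = 40%: 0.50 − 0.06 = 44 points.

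At these rates the difference widens only if 0.10 × c_P exceeds 0.50 × c_T, that is, if c_P is more than five times c_T. In simulation with a 20% chance of cut-off in each arm, the as-written estimate was below the exclusion estimate in about 95% of trials at 26/13 and 89% at 14/7. It was above it in about 5% and 9%.

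**6. Power.** Two-sided Fisher test by enumeration, with the exclusion result averaged over the random numbers kept. The 18/9 size is an assumption; 26/13 is the planned size.

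| Size | c | As written | Excluding |
|---|---|---|---|
| 18/9 | 13% | 32.9% | 34.5% |
| 18/9 | 22% | 23.6% | 29.6% |
| 26/13 | 13% | 59.2% | 58.2% |
| 26/13 | 22% | 49.7% | 52.7% |

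The gain from exclusion is small and can be slightly negative, because those observations are lost under either rule. Fisher's test is also only the SAP's fallback if the logistic model does not converge.

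**The case against.** The strongest reply is that the triggering event is not documented. SAP 15 names a small sample as the consequence of stopping and reports nobody taken off treatment. SAP 10.4 and 13, in the same SAP version, wait for all subjects to finish 12 weeks. That fits a halt to enrolment with enrolled women completing. Protocol 6.2 and 9.2 are standing contingency text and do not show that anyone was closed out. This stands: a reader might infer that women were in fact cut off and that the reported responder rates are biased, and the documents do not support that. They do leave the question open, and the rule depends on the answer.

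Other parts of the reply also stand:
- The share on treatment at the stop (19% to 30%) is not the share scored as failures, because mITT drops women with no post-baseline DHEAS.
- Attenuation is an expectation under similar cut-off in both arms. In a small 2:1 sample, chance imbalance can move the difference the other way.
- A response at Week 8 should still count in the separate Week 8 analysis, although SAP 13.2 does not say that the discontinuation rule applies only to visits after the stop.
- The study is exploratory, and SAP 10.6 already asks for caution in interpretation.
- Missing-as-failure is also a protocol rule, so an exception is a departure that must be recorded.

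None of this supplies a reason to score a sponsor's business decision as a woman's non-response.

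**Conclusion.** The gap is real and conditional. The SAP itself reports an early stop, keeps an unconditional non-responder rule, and does not reconcile the stop with its requirement that everyone complete 12 weeks. If any mITT woman was stopped for that reason, her later visits are scored as failures for a cause unrelated to response.

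Under even accrual over 40 to 64 weeks, close-out of everyone on treatment, similar cut-off in both arms and true rates of 50% and 10%, the 40-point difference is estimated at about 35 to 31 points. All of those inputs are assumptions. If nobody was stopped early, c is zero and nothing changes.

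Two stronger readings should be resisted. The rule cannot be said always to bias against the drug, since unequal cut-off can widen the difference. Nor does it undermine the primary result, because the primary DHEAS analysis does not use it. The case rests on bias in the responder estimate; loss of power adds little. The change should be made, but it concerns a secondary endpoint.

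**What to change.** - **SAP 13.2 and Table 3:** treat a responder visit not reached solely because the sponsor ended the study as administratively missing, and leave that woman out of that visit's denominator and model. Keep non-response for every other discontinuation, interruption or missing value.
- **Reporting:** give the number of such women per arm and visit, including an explicit zero if there were none. Show the rule as now written as a sensitivity analysis.
- **SAP 15:** record the departure from Protocol 8.3.4, and state whether enrolled women were allowed to finish.
- **SAP 10.4 and 13:** align the timing with SAP 15, for example by analysing once all subjects have completed Week 12 or been closed out.

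The cost is SAP wording, settled before unblinding, and a slightly smaller denominator at the affected visits. The fix depends on the recorded reason for withdrawal. Protocol 6.2 requires a primary reason on the eCRF, but the documents do not show that sponsor termination has its own category. If it does not, those cases need to be classified while treatment is still blinded.

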13.2.1 Statistical Hypotheses

For these secondary efficacy endpoints, the null hypothesis for the treatment comparison is that there is no difference in the proportion of responders in the tildacerfont treatment groups compared to the proportion of responders in the placebo treatment group after the 12-week, double-blind, placebo-controlled treatment period. The alternative hypothesis will be that there is a difference between the proportions of responders in each treatment group.

$$H_0: \pi_{tildacerfont} - \pi_{placebo} = 0;$$

$$H_A: \pi_{tildacerfont} - \pi_{placebo} \neq 0$$

13.2.1.1 Statistical Modeling and Testing

A logistic regression model will be used to evaluate whether the number of subjects who achieve control of DHEAS is different between the tildacerfont treatment groups and the placebo treatment group after 12 weeks of double-blinded, placebo-controlled, dose-escalating treatment. The model will include the responder indicator (Section 9.3.11) as the dependent variable for the Week 12 assessment; treatment group (0 = placebo, 1 = tildacerfont); age as well as baseline DHEAS (for Objective 2.1) or the multiple of baseline DHEAS x ULN (for Objective 2.2) as continuous covariates.

An exact score test derived from the logistic regression model, equivalent to an exact CMH test on small sample sizes, will be used to perform a two-sided test at a significance level of 0.05 to determine whether proportion of responders is different between the tildacerfont treatment group and the placebo treatment group at Week 12. If the logistic model does not converge, three Fisher's exact tests corresponding to tildacerfont compared to placebo will be utilized to assess if differences exist in the proportion of subjects meeting each of the responder criteria.

The statistical model used to characterize the secondary endpoints at Week 12 will also be used to characterize the tildacerfont response at earlier weeks, replacing the Week 12 outcome with the Week 8 and the Week 4 outcome.

Subjects with missing data are assumed to be non-responders in the secondary responder endpoints.

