
Statistical Methods:
 
Statistical Hypotheses
 
Efficacy endpoints will be evaluated using the following hypothesis-testing schema: Each tildacerfont dose will be compared with placebo. The null hypothesis will be that there is no difference in the endpoint between a given dose level of tildacerfont and placebo. The alternative hypothesis will be that there is a difference.
 
Sample Size
 
A sample size of 33 subjects with 2:1 randomization will provide at least 80% power to detect a difference of 164 mcg/dL in mean DHEAS between at least one dose of tildacerfont and placebo assuming a standard deviation of 154 mcg/dL and a two-sided alpha of 0.05. Accounting for a 15% drop out, the final sample size is N=39 (n=26 for tildacerfont group and n=13 for placebo). Subjects will be randomized using the strata of Screening DHEAS ($\leq 1.2 \times$ ULN, $> 1.2 \times$ ULN).
 
Analysis Populations
 
 The Intent-to-Treat (ITT) Population will include all subjects randomized in the study. The modified Intent-to-Treat (mITT) Population will include subjects in the ITT Population who have at least one dose of study drug, a baseline DHEAS assessment and at least one post baseline DHEAS assessment. The Safety Population will include all subjects who receive at least 1 dose of study drug in the study.

- The PK Population will include all randomized subjects who receive at least 1 dose of tildacerfont and have at least 1 evaluable PK sample.

Efficacy Analyses

All efficacy analyses will be conducted on mITT Population using a 2-sided alpha of 0.05. No adjustment for multiplicity is planned as this study is exploratory in nature.

The primary endpoint, the change from baseline in DHEAS, will be used to evaluate the preliminary efficacy of tildacerfont therapy relative to placebo and will be summarized using an analysis of covariance model (ANCOVA) with baseline DHEAS as a covariate and randomization strata and dose level as independent variables. Additional covariates may be added in the statistical analysis plan. The proportion of subjects meeting specific DHEAS thresholds will be summarized using exact tests through logistic regression using the randomization strata and dose level.

Exploratory hormone/androgen change endpoints will be analyzed using a similar methodology as the primary endpoint.

Safety Analyses

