10.8 Examination of Subgroups

Subjects will be categorized into the following common subgroups for the purposes of evaluating the primary and secondary efficacy endpoints. Due to the small sample size, subgroups will be summarized descriptively in place of subgroup analyses.

- Screening DHEAS ($\leq 1.2 \times \text{ULN}$; $> 1.2 \times \text{ULN}$)
- Inclusion Criteria #3: “DHEAS level $>$ age-matched reference ULN at the screening visit.” (Subjects enrolled into the study fully compliant with inclusion/exclusion criteria; subjects who marginally do not meet inclusion criteria #3)

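### The responder p-value comes from an exact test conditioned on continuous covariates; it is not an exact CMH test, and in a small sample p<0.05 can be out of reach while the Fisher fallback stays off

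*SAP*

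**What the plan says.** SAP 13.2.1.1 fits a logistic model with treatment group and, in its words, "age as well as baseline DHEAS (for Objective 2.1) or the multiple of baseline DHEAS x ULN (for Objective 2.2) as continuous covariates". The two-sided 0.05 decision rests on "An exact score test derived from the logistic regression model, equivalent to an exact CMH test on small sample sizes". Fisher's exact test replaces it only under one condition: "If the logistic model does not converge". The same model serves Weeks 12, 8 and 4, and SAP 13.2.1.3 repeats it for 25% and 20% reductions.

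SAP 10.1 leaves the screening-DHEAS stratum out of models whose outcome is derived from DHEAS, so no categorical stratum remains.

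The protocol is not uniform. Its synopsis says the proportions "will be summarized using exact tests through logistic regression using the randomization strata and dose level". Section 8.3.4 has "exact tests through logistic regression using a similar variable structure as the primary endpoint" and lets the SAP add covariates.

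SAP 15 records early discontinuation and drops the modelled exploratory analyses, giving the reason "Due to the resulting small sample size". It states no final n and does not list the change of covariates in the responder model.

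**The concern.** An exact test from logistic regression eliminates the nuisance parameters by conditioning on their sufficient statistics. If the only nuisance terms are stratum indicators, this fixes the number of responders in each stratum, and the result is the exact CMH test. If they are continuous age and baseline DHEAS, it fixes the number of responders and the totals of age and of DHEAS among responders. Few alternative response patterns match all three, and in a small trial the reference set can shrink to one or two points.

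Convergence does not protect against this: maximum likelihood can converge on data whose exact conditional distribution is almost degenerate. Zero placebo responders separates the data and plausibly leads to Fisher's test, whereas a single placebo responder may leave a test that cannot reject. The SAP does not say whether separation counts as non-convergence.

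Placebo responders on the DHEAS ≤ ULN endpoint (Objective 2.2) are plausible. SAP 10.8 mentions "subjects who marginally do not meet inclusion criteria #3", and SAP 15 says "some subjects have entered the study up to 25% lower than anticipated DHEAS". If note [2] to SAP Table 1 restricts 2.2 to subjects entering above ULN, its n is smaller still.

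At stake are four responder definitions (30%, 25%, 20%, ≤ ULN) at three visits, 4 × 3 = 12 tests.

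**Working it through.** **The plan's own figure.** Power is given only for the primary endpoint. With a difference of 164, SD 154 and 2:1 allocation, the placebo n is (1 + 1/2) × (154/164)² × (1.960 + 0.842)² = 10.4, so 11 + 22 = 33. Power is 82.2% by the normal approximation and 79.8% by the t-test. 33/0.85 = 38.8, so 39. The plan is reproduced, but it gives no response rate or power for the responder endpoints.

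**The equivalence claim.** Take one simulated set of 15 subjects, with 8/10 responders on active and 1/5 on placebo:

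| Conditioning on | Patterns in reference set | p | Smallest attainable p |
|---|---|---|---|
| responder count only | 5005 | 0.0889 | 0.0020 |
| screening-DHEAS stratum | 1960 | 0.0510 (exact CMH: 0.0510) | 0.0026 |
| age and DHEAS | 2 | 1.0 | 1.0 |

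**Attainability.** For each simulated 2:1 trial, all response patterns with the observed Σy, Σy·age and Σy·DHEAS were counted. The two-sided p is the share of patterns with |T − E(T)| at least as large as observed, where T is the number of active responders. Only trials without complete or quasi-complete separation are counted here. Age is in whole years from 18 to 40 (SAP 9.3.5), ULN is 377 or 295 (SAP Table 2), and DHEAS is capped at 650 (exclusion criterion 2). The baseline distribution and response rates are assumed. Share of trials where p<0.05 is unattainable, Objective 2.1, whole-number DHEAS:

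| n | 50 v 5, 65 v 15, 75 v 25% (baseline 1.0–1.7 × ULN) | 70 v 15% (baseline from about 0.9 × ULN) | 65 v 15%, separate run |
|---|---|---|---|
| 18 | 100% | 100% | 100% |
| 21 | 94–98% | 93% | 98% |
| 24 | 36–57% | 33% | 28% |
| 27 | 5–17% | 4% | 8% |

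Median reference sets in the last run were 2, 8, 62 and 238 patterns. With DHEAS to 0.1 mcg/dL (70 v 15%), the shares are 100%, 99%, 37%, 6% and 0% at n=21, 24, 27, 30 and 33.

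Objective 2.2, reading the covariate as DHEAS/ULN:
- Unrounded: 100% up to n=24, 99% at n=27, 20–52% at n=33.
- Two decimals: 99% to about 100% at n=18, 51–69% at n=21, 10–24% at n=24, 1–6% at n=27.

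The unrounded ratio is harsher because the two limits share no common factor. If the responders' DHEAS totals change by a (aged 30 or under) and b (31 to 40), then a/377 + b/295 = 0 requires a = 377k and b = −295k for a whole number k.

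**Power on the reading most favourable to the SAP** (Fisher's p used in every separated trial; first set of assumptions; 1000 trials per cell at n=18 and 21, 600 at 27, 400 at 33):

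| n | Response | 2.1 | 2.2 unrounded | 2.2, 2 decimals | Stratified exact | Fisher |
|---|---|---|---|---|---|---|
| 18 | 50 v 5% | 28 | 28 | 28 | 28 | 29 |
| 18 | 65 v 15% | 31 | 31 | 31 | 40 | 43 |
| 18 | 75 v 25% | 20 | 20 | 20 | 42 | 46 |
| 21 | 50 v 5% | 41 | 41 | 43 | 39 | 44 |
| 21 | 65 v 15% | 33 | 32 | 41 | 47 | 48 |
| 21 | 75 v 25% | 16 | 15 | 29 | 47 | 47 |
| 27 | 50 v 5% | 61 | 50 | 62 | 63 | 65 |
| 27 | 65 v 15% | 58 | 22 | 61 | 65 | 69 |
| 27 | 75 v 25% | 53 | 7 | 59 | 64 | 68 |
| 33 | 50 v 5% | 74 | 68 | 73 | 73 | 74 |
| 33 | 65 v 15% | 74 | 57 | 75 | 74 | 78 |
| 33 | 75 v 25% | 70 | 38 | 71 | 69 | 69 |

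At n=18 to 27 for 2.1, power falls as placebo response rises even though the difference widens slightly, because fewer trials reach the fallback. With 7 placebo subjects, the chance of no placebo responder is 0.95⁷ = 70%, 0.85⁷ = 32% and 0.75⁷ = 13%. If separation is not treated as non-convergence, power at n=21 is 2–3% for 2.1, 0% for 2.2 unrounded and 14–25% for 2.2 at two decimals.

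**Sensitivity.** With baseline down to 0.75 × ULN (65 v 15%), power for 2.1 / 2.2 unrounded / two decimals is 32/32/38 against 45 stratified at n=21, and 59/22/61 against 64 at n=27.

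**The case against.** The strongest reply concerns size. The final n is unknown, and at the planned 33 Objective 2.1 loses nothing. DHEAS was chosen as a stable marker (Protocol 1.2.1), so few placebo subjects may fall by 30%. When response was instead generated from an assumed lognormal change in DHEAS, placebo response came out at 1–8%. Power for 2.1, SAP test against stratified exact, was then 68/66, 38/42 and 10/12 at n=18; 87/81, 49/48 and 20/16 at n=21; and 94/94, 65/66 and 29/26 at n=27, so nothing material is gained there. That stands for the 30% threshold. The 25% and 20% thresholds, where placebo response should be higher, were not tested, and 2.2 lost power in the same exercise.

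The extreme 2.2 figures need an unrounded ratio. That also stands: they are one end of a range. But a rounding convention the SAP does not state should not decide whether a test can reject. Restricting 2.2 to subjects entering above ULN would lower placebo response and make the fallback more likely, but it would also cut n.

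SAP 13.2.1.2 also reports proportions, differences, confidence intervals and odds ratios with nominal p-values, and SAP 10.6 calls the study exploratory. This limits the harm, but those outputs do not replace the test that carries the 0.05 decision.

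Finally, SAP 10.1 discloses and partly explains the covariate choice, and the protocol allows it. That defends adjusting the model, not the equivalence claim or the fallback rule.

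**Conclusion.** The concern holds. The equivalence statement is wrong at any sample size, because the model contains no categorical stratum. The fallback is incomplete, because it ignores a degenerate exact distribution in a model that converges.

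The practical loss depends on n, placebo response and recorded precision. For 2.1 with whole-number DHEAS, it is severe at n=18 to 21 once placebo responders occur (16–33% power against 40–47% in the 15% and 25% placebo scenarios). It fades between about n=24 and n=33 and is negligible at 33. For 2.2 with an unrounded ratio it persists at n=33 (38–68% against 69–74%). Below about n=15 no alternative fully helps: at n=12 (70 v 15%, non-separated trials), p<0.05 is unattainable in 25% of trials with Fisher and 33% with the stratified test.

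These sizes rest on assumed response rates, baseline distributions and n, and on the conditional reading of the exact test. The consequence is an uninformative p-value beside a visible difference, and a test that can change with one placebo responder. The SAP should be changed, but the trial's overall interpretation does not hinge on it.

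**What to change.** Before unblinding, name one test for all responder analyses, not just as a fallback: either an exact test stratified by the two-level screening-DHEAS factor (the protocol synopsis structure) or Fisher's exact test. For an adjusted odds ratio and interval, use Firth-penalised logistic regression with age and baseline DHEAS, and state that its interval may disagree with the exact p-value. Delete the CMH wording for the continuous-covariate model, align SAP 10.1, and list the change in SAP 15.

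If the sponsor keeps the present model, the minimum is to state that separation or a degenerate exact distribution triggers one named fallback, to fix the precision of DHEAS/ULN, and to remove the equivalence claim.

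The cost is wording in SAP 10.1, 13.2.1.1 and 15, with standard software options. The p-value would no longer adjust for continuous age and baseline. The stratified test is up to 5 points less powerful than Fisher's (39 v 44 at n=21, 50 v 5%). Nothing is gained where placebo response is near zero and Fisher's test would apply anyway.
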